4.5 Study Duration and End of Trial

For each participant, the study duration will be approximately either 13 weeks (Part 1), or 19 weeks (Part 2). This includes a post treatment period of 6 weeks following the final MGD014 infusion through end of study, which is approximately 5 times the anticipated 8-day half-life based on preclinical animal studies. As participant accrual will be staggered so that the full 2-week DLT period will occur prior to dose escalation in Part 1, the overall study duration will be approximately 36 months. The end of trial is the date that all participants enrolled have completed their end of study visit. The end of trial is when the clinical study database is locked after the last participant in the study completes discharge procedures at the last visit and the study forms have been entered, monitored, reviewed, and approved by PI.

4.5.1 Definition of End of Study

The end of study will occur after the last patient has met off-study criteria and the data collection process is completed (time of study database lock).

End of study for each patient is defined as follows: The date that the participant meets discontinuation criteria or is lost to follow-up.

5 STUDY PROCEDURES

The eligibility criteria for this study have been carefully considered to ensure the safety of the study participants and to ensure that the results of the study can be used. It is imperative that participants meet all eligibility criteria and qualifications to participate in the study. No exceptions to these criteria will be granted by the sponsor.

5.1 Inclusion Criteria

1. Aged \geq 18 years and \leq 65 years of age.
2. Ability and willingness of participant to provide written informed consent.

Note: Due to the lack of foreseeable benefit to study participants, no enrollment of illiterate or mentally incompetent persons allowed.

3. HIV-1 infection, documented by any FDA-approved rapid HIV test or HIV enzyme or chemiluminescence immunoassay (E/CIA) test kit at any time prior to study entry and confirmed by a licensed Western blot or a second antibody test by a method other than the initial rapid HIV and/or E/CIA, or by HIV-1 antigen, plasma HIV-1 RNA viral load.

Note: The term “licensed” refers to a US FDA-approved kit, which is required for all investigational new drug studies.

The World Health Organization and Centers for Disease Control and Prevention guidelines mandate confirmation of the initial test result with a second distinct assay. For example, a reactive initial rapid test should be confirmed by either another type of rapid assay or an E/CIA that is based on a different antigen preparation and/or different test principle (e.g., indirect versus competitive), or a Western blot or a plasma HIV-1 RNA assay.

4. On continuous antiretroviral therapy (ART defined below) for at least 24 months prior to screening.

Note: For study eligibility – participant must not have missed more than 9 total days in the 3 months prior to screening.

5. Permitted ART regimens include:

- a. At least 3 ART agents (not counting ritonavir if less than 200 mg total daily dose or cobicistat as one of the agents).

Note: One of the agents must include an integrase inhibitor, NNRTI (Non-Nucleoside Reverse Transcriptase Inhibitors), or a protease inhibitor.

OR

- b. Two (2) ART agents in which one of the agents is either a boosted protease inhibitor or an integrase inhibitor, that are FDA approved or are recommended by the Department of Health and Human Service Treatment Guidelines.

Note: Other potent fully suppressive antiretroviral combinations will be considered on a case-by-case basis.

Note: Changes in drug formulation or dose are allowed (e.g., tenofovir disoproxil fumarate (TDF) to tenofovir alafenamide (TAF), ritonavir to cobicistat, or separate ART agent dosing to fixed-dose combination), but none within 30 days prior to screening.

Note: Prior changes in, or elimination of, medications for easier dosing schedule, intolerance, toxicity, improved side effect profile or within a drug class are permitted but none within 30 days prior to screening if an alternative suppressive regimen was maintained.

6. Able and willing to adhere to protocol therapy and treatment schedule.
7. Agrees not to enroll in another study of an investigational research agent for the duration of the participant's study participation.
8. Plasma HIV-1 RNA viral load < 50 copies/mL at two time points in the previous 12 months prior to screening (one time point can be screening) and never \geq 50 copies/mL on 2 consecutive time points in the last 24 months.

Note: The documented plasma HIV-1 RNA viral load must be performed by any United States laboratory that has a Clinical Laboratory Improvement Amendments (CLIA) certification or its equivalent certification or accreditation.

9. Plasma HIV-1 RNA viral load < 50 copies/mL obtained at screening, performed at US laboratory that has a CLIA certification or its equivalent certification or accreditation.
10. CD4 cell count $>$ 350 cells/mm³ obtained at screening, performed at any US laboratory that has a CLIA certification or an equivalent certification or accreditation.
11. Hepatitis C virus (HCV) antibody negative result at study screening or, if the HCV antibody result is positive, a negative HCV RNA result at study screening.
12. Negative Hepatitis B surface antigen result obtained at study screening.
13. When participating in sexual activity that could lead to pregnancy, male participants with partners of childbearing potential must agree to consistently use 2 reliable forms of contraception simultaneously from the time of consent through 6 months after their last infusion of study drug. Such methods include: condoms (male or female) with or without a spermicidal agent; diaphragm or cervical cap with spermicide; intrauterine device (IUD); hormone-based contraception. NOTE: For female partners who are receiving ritonavir or cobicistat, estrogen-based contraceptives are not reliable and an alternative method should be suggested.
14. Ability and willingness of participant to continue ART throughout the study.
15. Ability and willingness to provide adequate locator information.
16. Ability and willingness to communicate effectively with study personnel; considered reliable, willing, and cooperative in terms of compliance with the protocol requirements.

17. Adequate vascular access for MGD014 infusion and leukapheresis.

Exception: Participants who opt out of the leukapheresis procedure, are not required to have adequate vascular access for a leukapheresis procedure.

18. Participant must have adequate organ function as indicated by the following laboratory values, at the screening visit:

Laboratory Values Required for Study Eligibility	
Test Name	Laboratory Value
Hematological	
Absolute neutrophil count	$\geq 1,500 / \mu\text{L}$
Platelets	$\geq 125,000 / \mu\text{L}$
Hemoglobin	$\geq 12 \text{ g/dL} (\text{male}) \text{ and } \geq 11 \text{ g/dL} (\text{females})$
Coagulation	
Prothrombin Time or INR	$\leq 1.1 \times \text{ULN}$
Chemistry	
K ⁺ levels	Within normal limits
Mg ⁺⁺ levels	Within normal limits
Glucose	Screening serum glucose \leq Grade 1 (fasting or non-fasting)
Albumin	$\geq 3.5 \text{ g/dL}$
Renal	
Creatinine clearance determined by the CKD-Epi equation found at: https://www.qxmd.com/calculate/calculator_251/egfr-using-ckd-epi	eGFR $> 60 \text{ mL/min}$
Hepatic	
Serum total bilirubin	Total bilirubin < 1.5 times the ULN range. If total bilirubin is elevated, direct bilirubin must be < 2 times the ULN range. NOTE: If participant is on an atazanavir-containing therapy, then a direct bilirubin should be measured instead of the total bilirubin and must be $\leq 1.0 \text{ mg/dL}$.
AST and ALT	$\leq 1.25 \times \text{ULN}$
ALK-P	$\leq 1.25 \times \text{ULN}$
Lipase	$< 1.1 \times \text{ULN}$
Serum Pregnancy	Negative

Abbreviations: ALK-P = Alkaline Phosphatase; ALT = Alanine Transaminase; AST = aspartate aminotransferase; CKD-Epi = Chronic Kidney Disease Epidemiology Collaboration; eGFR = estimated glomerular filtration rate; INR = international normalized ratio; K⁺ = potassium; Mg⁺⁺ = magnesium; ULN = upper limit of normal.

Labs/procedures completed during a routine clinical care appointment that are the same as the study screening labs and/or procedures and completed within the 14 days preceding the screening visit can be used to qualify the participant upon approval by the study PI or designee.

5.2 Exclusion Criteria

1. Women of Child-Bearing Potential (WOCBP) are excluded as the in vivo teratogenic potential of this compound is unknown. WOCBP include any female who has experienced menarche and who has not undergone successful surgical sterilization or menopause.
 - a. WOCBP must have documentation from a medical record or physician of successful surgical sterilization, i.e. hysterectomy, bilateral tubal ligation, ESSURE procedure, or bilateral oophorectomy
 - b. Post menopause is defined as: amenorrhea \geq 12 consecutive months without another cause or, for women with irregular menstrual periods and on hormone replacement therapy, a documented serum follicle stimulating hormone (FSH) level > 35 mIU/mL.
2. Any HIV-1 RNA viral load > 1000 copies/mL within 6 months prior to screening.
3. History or other evidence of severe illness, immunodeficiency other than HIV, or any other condition that would make the potential participant unsuitable for study in the opinion of the PI (or designee).
4. History or other evidence of any condition or process for which signs or symptoms could be confused with reactions to MGD014.
5. History of any HIV immunotherapy or HIV vaccine except for MGD014 within 12 months prior to screening.
6. History of clinically significant cardiovascular disease including, but not limited to:
 - a. Myocardial infarction or unstable angina within the 6 months prior to the initiation of study drug.
 - b. Clinically significant cardiac arrhythmias.
 - c. Uncontrolled hypertension: systolic blood pressure (SBP) > 180 mmHg, diastolic blood pressure (DBP) > 100 mmHg that is sustained on repeat measurement (without intervention).
 - d. Deep vein thrombosis, pulmonary embolism, stroke, or transient ischemic attack within the 6 months prior to the initiation of study drug.
 - e. QTc prolongation > 480 msec.
 - f. Congestive heart failure (New York Heart Association class III-IV).
 - g. Pericarditis/clinically significant pericardial effusion.
 - h. Myocarditis.

7. Evidence of active viral, bacterial, or systemic fungal infection requiring parenteral antibiotic, antiviral, or antifungal treatment within 7 days prior to the initiation of study drug. Participants requiring any systemic antiviral, antifungal, or antibacterial therapy for active infection must have completed treatment no less than one week prior to the initiation of study drug
8. Active COVID-19/SARS-CoV-2 infection. While SARS-CoV-2 testing is not mandatory for study entry, testing should follow local clinical practice guidelines/standards. Participants with a positive test result for SARS-CoV-2 infection, known asymptomatic infection, or suspected infection are excluded.
9. Active, untreated syphilis (defined as rapid plasma reagins (RPR) positive at screening visit, without any documented history of appropriate treatment).

Note: If positive at screening without history of treatment, participant will be allowed one rescreen following documentation of recent, appropriate treatment.

10. Known allergic hypersensitivity to recombinant proteins, or any excipient contained in the drug or vehicle formulation for MGD014.
11. History of a severe allergic reaction with generalized urticarial, angioedema, or anaphylaxis within 2 years of study entry or history of hereditary angioedema, acquired angioedema, or idiopathic angioedema.
12. History of malignancy within the past 5 years or current malignancy that may require chemotherapy or radiation therapy.

Note: a history of non-melanoma skin cancer (e.g. basal cell carcinoma or squamous cell skin cancer) with documentation of complete resection or resolution per licensed and board-certified dermatology consultant following topical therapy is not exclusionary.

13. Seizure disorder: History of seizure(s) within the past two years.
Note: history of seizure disorder controlled on anti-epileptic therapy, with no seizure within the past two years, does not exclude participant.
14. History of organ or tissue transplantation.
15. History of autoimmune disease, including type I diabetes mellitus, with the specific exceptions of:
 - a. Vitiligo.
 - b. Resolved childhood atopic dermatitis.
 - c. Psoriasis (with the exception of psoriatic arthritis) not requiring systemic treatment (within the past 2 years).
 - d. Graves disease with subsequent return to a euthyroid state (clinically and by laboratory testing).

16. Known psychiatric or substance abuse disorders that preclude compliance with the protocol as assessed by the study PI (or designee). Specifically excluded are persons with psychoses within the past 3 years, ongoing risk for suicide, or history of suicide attempt or gesture within the past 3 years.
17. Participation in another investigational clinical research study (with the exception of an antiretroviral treatment trial that uses FDA approved antiretroviral agents) within 60 days prior to study screening.

Note: Co-enrollment in the ACTG 5332 REPRIEVE study (NCT02344290) and using FDA approved pitavastatin is permitted provided participant enrolled on ACTG 5332 and has taken the study provided medication \geq 4 months.

Note: Enrollment in investigative trials using FDA approved medications may be reviewed on a case-by-case basis.

18. History of unstable asthma, including sudden acute attacks occurring without an obvious trigger or asthma requiring hospitalization. Additional criteria for exclusion include:
In the past year has either of the following:
 - a. >1 exacerbation of symptoms treated with oral/parenteral corticosteroids;
 - b. Emergency care, urgent care, hospitalization, or intubation for asthma.
19. Bleeding disorder diagnosed by a doctor (e.g., clotting factor deficiency, coagulopathy, or platelet disorder requiring special precautions).
20. Use of any of the following within 90 days prior to screening: receipt of any blood product, immune globulin, immunomodulatory therapy, cytokine therapy, or growth stimulating factors such as systemic corticosteroids, cyclosporine, methotrexate, azathioprine, anti-CD25 antibody, interferon (IFN), interleukin-2 (IL-2), systemic cytotoxic chemotherapy, or investigational therapy. Intent to use immunomodulators (e.g., IL-2, IL-12, interferons or TNF modifiers) during the course of the study.
21. Current use of the following antiretrovirals: maraviroc and/or enfuvirtide.
22. Positive ADA (anti-MGD014) obtained during screening in Part 2.
23. Any vaccination with the exception of the flu vaccine, within 30 days prior to screening.

Note: Individuals who require vaccination will delay screening for the study until 30 days after receiving the last injection.

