Anti-drug antibodies (ADA) were confirmed in 10 out of 30 animals that received administration of MGD014. Of these, ADA was first detected in 4 animals during the dosing period (between Days 29 and 36) and in 6 animals during the recovery period (between Days 50 and 91). Although ADA were detected in 10 animals, no obvious changes in the PK profile were observed in these animals except for one animal from the 10 mg/kg dose group.

There were no noteworthy MGD014-related increases in serum concentrations of cytokines (IFN- γ , IL-2, IL-4, IL-5, IL-10, or TNF- α).

There also were no noteworthy MGD014-related changes in the frequencies of circulating CD4 and CD8 T cells, nor in the frequencies of CD4 and CD8 T cells expressing markers of activation or exhaustion (CD25, CD69, PD-1, TIM-3), as determined by flow cytometry. Assessment of MGD014 binding to CD4 and CD8 T cells demonstrated that binding to CD3 was 1-2% of maximal at 0.1 mg/kg, ~30% of maximal at 1 mg/kg, and maximal at 10 mg/kg, when measured at 24-hours post-infusion. Binding to CD3 was transient and nearly completely reversed for the low- and mid-dose groups and ~50% reversed for the high-dose group by 7-days post-infusion.

Based on these results, the no-observed-adverse-effect level (NOAEL) was considered to be 10 mg/kg/dose, which correlated to C_{max} of 180 μ g/mL and AUC_{last} of 5604 hr• μ g/mL.

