9.3 Screening Period

Screening evaluations will be performed within 8 weeks (56 days) prior to study drug administration on Day 0 unless otherwise specified. At the 1st screening visit, participants will screen for the study. Only those participants who meet all eligibility criteria specified in [Section 5.1](#) Inclusion Criteria and [Section 5.2](#) Exclusion Criteria will be enrolled. A unique PID will be assigned during the screening visit. Participants who had previously completed Part 1 and are being considered for Part 2 will maintain the same PID and will be assigned a new study-specific identifier (SID).

Participants who are unable to meet protocol defined eligibility criteria at the Screening Visit (Step 1, Visit 1) may be eligible to re-screen again at the PI (or designee)'s discretion. In such cases, the same PID will be used. If a screen failure or the failure to enroll is due to the inability to meet one of the laboratory parameters (hematology, chemistry, HIV RNA, or CD4 T cell count), a laboratory retest of the failed criteria may be performed one time only. If the repeat value is within eligibility requirements, the participant can enroll on the study.

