Visits	1	2	3	4	5	6	7	8	9	10	11
Visit Event	Screen	Enroll ²	Day 0	Day 1	Day 3	Day 14	Day 28	Day 42	Day 49	Day 63	Day 77
Study Weeks	Within 8 weeks of Day 0	0	1	1	2	4	6	7	9	11	
Window period (+ or – days)		≤ 56d screen	≤ 56d screen	0	0	1	1	1	1	3	3
Study Drug Administration											
MGD014 ⁴			X			X	X				
Clinical Procedures											
Informed Consent ¹	X										
Collect Locator information	X										
Assign PID ⁵	X										
Enrollment/Assign SID ⁶		X									
Medical History ⁸	X										
Physical Exam ⁹	X										X
Vital signs ¹⁰	X	X	X	X	X	X	X	X	X	X	
Weight	X	X	X			X	X				
Height	X										
PI review of ART treatment history ¹¹	X										
Directed Physical Assessment ¹²			X	X	X	X	X	X	X	X	
Assess ART and ART adherence ¹³	X	X	X	X	X	X	X	X	X	X	X
Assess venous access	X										
Concomitant Medications ¹⁴	X	X	X	X	X	X	X	X	X	X	
ECG ¹⁵	X		X			X	X				X
Signs, symptoms and diagnosis of illnesses and diseases ¹⁶		X	X	X	X	X	X	X	X	X	X
Pre-Infusion Medications ¹⁷			X			X	X				
Assess for Adverse Events		X	X	X	X	X	X	X	X	X	X
Post-Infusion Assessment ¹⁸			X	X	X	X	X				
Optional Leukapheresis ²³		X						X			

Part 2	Step 1 Pre-Treatment		Step 2 – Treatment					Step 3 – Post Treatment			End of Study ³	
	Visits	1	2	3	4	5	6	7	8	9	10	
Clinical Lab Procedures												
CBC with differential	X	X ²²	X			X	X	X ²²		X	X	
Chemistry Panel ¹⁹	X		X			X	X			X	X	
Calculated Creatinine Clearance	X											
Albumin & Lipase	X									X	X	
Fasting Lipids & Triglycerides	X									X	X	
Pregnancy test (serum) ²⁰	X											
Pregnancy test (urine/POCT) ²⁰			X			X	X			X		
FSH; optional for proof of menopause	X											
PT, INR and aPTT	X										X	
CD4/CD8	X										X	
HIV-1 RNA	X										X	
RPR	X											
Hepatitis B and Hepatitis C	X											
Complete Urinalysis with microscopic exam	X											
Research Laboratory Sample Collection												
HLA		X										
Anti-Drug Antibody (ADA) ²¹	X					X	X				X	
Pharmacokinetics (PK) ²¹			X	X	X	X	X	X			X	
PD: Receptor Occupancy (RO) Measurements ²¹			X	X		X	X				X	
PD: Serum Cytokines ²¹			X	X	X	X	X					
PD: T Cell Phenotype ²¹			X	X		X	X				X	
Resting CD4 T Cell Infection by QVOA ²³		X						X				
Single Copy Assay ²³		X		X				X			X	

1 **Consent:** Obtain prior to obtaining any study-associated procedure.

2 **Study Enrollment:** Determination of study eligibility by the inclusion and exclusion criteria occurs in the Step 1, Visit 1 Screening.

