Note: Actual start and end of infusion times, PK, and ADA sample collection times will be recorded on the source documents. All sample time points are hours after EOI, unless otherwise specified. Samples required at EOI can be drawn up to 5 minutes before the infusion is complete, post EOI samples can be drawn +/- 5 minutes; duration of infusion = 120 minutes. 24 - and 48-hour samples will be drawn on Day 1 and 2 respectively.

Abbreviations: ADA = Anti-drug antibody; EOI = end of infusion; PK = Pharmacokinetic.

PART 2 Pharmacokinetics, Immunogenicity, and Pharmacodynamic Biomarkers Blood Sampling Schedule for MGD014						
MGD014 Dosing	Treatment Day	PK ^a Sampling Time (Hours)	ADA Sampling Time (Hours)	Receptor Occupancy ^b (Hours)	Serum Cytokines ^c (Hours)	T cell Phenotype (Hours)
X	0	0 ^d (Pre-infusion)		0 ^d (Pre-infusion)	0 ^d (Pre-infusion)	0 ^d (Pre-infusion)
	0	EOI				
	0	1 (post EOI)				
	0	4 (post EOI)		4 (post EOI)	4 (post EOI)	4 (post EOI)
	1	24 +/- 5 hours (post EOI)		24 +/- 5 hours (post EOI)	24 +/- 5 hours (post EOI)	24 +/- 5 hours (post EOI)
	3	72 +/- 5 hours (post EOI)			72 +/- 5 hours (post EOI)	
X	14	0 (Pre-infusion)	0 (Pre-infusion)	0 (Pre-infusion)		0 (Pre-infusion)
	14	EOI		4 (post EOI)	4 (post EOI)	4 (post EOI)
X	28	0 (Pre-infusion)	0 (Pre-infusion)	0 (Pre-infusion)		0 (Pre-infusion)
	28	EOI		4 (post EOI)	4 (post EOI)	4 (post EOI)
	42	1008 hours +/- 1 day				
	77 (EOS visit)	1848 hours +/- 3 days	X	X		X

- a Do not collect PK samples from infusion port. Obtain PK samples as follows: Pre-infusion: Before start of infusion on visit day (dosing day) or day before. When collecting multiple samples, collect the PK sample first.
- b If at any time in Step 3 RO reaches below the limit of detection, at the discretion of the PI or designee, further measurement of RO may be deemed unnecessary.
- c Additional samples may be obtained selectively at additional time points in participants who experience signs and symptoms of cytokine release.
- d All pre-dose PK, ADA, Receptor Occupancy including T-cell binding, cytokines, and T-cell Phenotype samples will be collected prior to start of MGD014 infusion; the start of MGD014 infusion is designated as time = 0 hour.

Abbreviations: ADA = Anti-drug antibody; EOI = end of infusion; PK = Pharmacokinetic.

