4.12 Immunogenicity Endpoints and Analyses

The proportion of participants who are negative for MGD014 ADA at baseline and become positive in this assay, the proportion of participants who are negative at baseline and remain negative, and those who have positive ADA at baseline that increases or decreases in titer over the course of treatment will be summarized. Positive samples will be evaluated for neutralizing capacity and the incidence of neutralizing antibodies will also be summarized. The impact of immunogenicity on safety, PK, and PD will be summarized and explored graphically.

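### Part 2 has no Day 0 ADA sample and no defined ADA baseline, so antibody induced by a returner's Part 1 dose could be counted as a multi-dose conversion

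*Protocol*

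**What the plan says.** - **Eligibility.** Exclusion 22 (Protocol 5.2) removes people with "Positive ADA (anti-MGD014) obtained during screening in Part 2". For those coming from Part 1, Protocol 4.3 adds a second condition: no detectable ADA when Part 1 ends, which is the Day 42 visit.
- **Age of the screening sample.** Protocol 9.3: "Screening evaluations will be performed within 8 weeks (56 days) prior to study drug administration on Day 0 unless otherwise specified".
- **Part 2 ADA schedule.** Appendix 1 marks ADA at screening, Day 14, Day 28 and Day 77. Appendix 2 has ADA before the Day 14 and Day 28 infusions and at Day 77. Its Day 0 pre-infusion row is filled for PK, receptor occupancy, cytokines and T-cell phenotype, and is blank for ADA.
- **Footnote d to that Appendix 2 table.** "All pre-dose PK, ADA, Receptor Occupancy including T-cell binding, cytokines, and T-cell Phenotype samples will be collected prior to start of MGD014 infusion". In Part 1, where footnote c carries the same wording, the Day 0 pre-infusion ADA cell is filled.
- **Endpoint.** SAP 4.12, matching Protocol 14.8, summarises "The proportion of participants who are negative for MGD014 ADA at baseline and become positive in this assay", those who stay negative, and those positive at baseline whose titre changes. Neither section defines baseline for Part 2 or for a person who was in Part 1.
- **Other eligibility text.** Exclusion 20 bars investigational therapy in the 90 days before screening and writes no exception for MGD014. Exclusion 5, on HIV immunotherapy, does except MGD014.

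**The concern.** Part 2 is the part that admits people already exposed to MGD014, and it is the part without an ADA sample at its own Day 0. If antibody to the Part 1 dose becomes detectable after the Part 2 screening sample, no scheduled sample can show that it was there before the multi-dose regimen began. The next result comes on Day 14, one infusion later.

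Immunogenicity is a secondary objective. If the screening sample serves as baseline, exclusion 22 leaves the positive-at-baseline category empty for Part 2, and a Day 14 positive falls into the conversion category by default. The plan also promises to explore the effect of ADA on PK. The only dense Part 2 PK profile follows the first infusion (end of infusion, 1, 4, 24 and 72 hours), where there is no ADA result from the same day.

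**Working it through.** **1. Length of the unsampled interval.** The plan's own figure reproduces: 8 weeks × 7 = 56 days from screening to Day 0.
- Screening to next ADA sample: 56 + 14 = 70 days, or 71 with the ±1-day window at Day 14.
- With a Day 0 sample: 0 days to first infusion, and 14 to 15 days to the next sample.

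**2. Parts 1 and 2 side by side.**

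| | Part 1 | Part 2 |
|---|---|---|
| Previously exposed people admitted | not addressed | yes (4.3) |
| Footnote lists ADA among pre-dose samples | yes (c) | yes (d) |
| Day 0 pre-infusion ADA cell | filled | blank |
| Baseline defined for the ADA endpoint | no | no |

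**3. When a returner could be screened and infused, in days from the Part 1 infusion.**
- *Exclusion 20 not applied to MGD014:* screening from about Day 42; Part 2 Day 0 up to 42 + 56 = Day 98 (93 to 103 with the ±5-day window).
- *Exclusion 20 applied as worded:* screening from Day 90; for someone screened then, Part 2 Day 0 up to 90 + 56 = Day 146.

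The only onset data in the documents are from monkeys (Protocol 2.2.2). ADA was found in 10 of 30 treated animals: 4 first positive on Days 29 to 36, and 6 on Days 50 to 91 (6/30 = 20%). Under the first reading, the interval from Day 42 to Day 98 spans that whole later range. Under the second, screening comes after nearly all of it, and the documents contain no onset later than Day 91.

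The analogy is loose. The animals had six weekly doses. If the first was on Day 1, the last was on about Day 36, so Days 50 to 91 lie 50 − 36 = 14 to 91 − 36 = 55 days after the last dose. A Part 1 participant has one dose and a test at Day 42, which falls inside that range.

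**4. Effect of one case on the reported rate (Clopper-Pearson 95% intervals).**
- Part 2 alone, n = 6: from 0/6 = 0% (0 to 46%) to 1/6 = 16.7% (0.4 to 64%).
- All of about 26 participants pooled: 1/26 = 3.8 points.

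**5. Chance of at least one case.** The formula is 1 − (1 − p)^k, for k returners who each have probability p of converting between screening and Day 0. Neither p nor k is in the documents; both are assumed.

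| p | k = 1 | k = 3 | k = 6 |
|---|---|---|---|
| 1% | 1% | 3% | 6% |
| 5% | 5% | 14% | 26% |
| 20% | 20% | 49% | 74% |

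**The case against.** The strongest reply is that the affected returner may hardly exist.

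- **Exclusion 20.** Read literally, it keeps a returner from being screened until 90 days after the Part 1 dose. It also names immunomodulatory therapy, and Protocol 7.1 describes MGD014 in such terms. This stands as a reason to think late conversion much less likely, if the criterion applies. The express MGD014 exception in exclusion 5 makes that uncertain.
- **Part 1 spacing.** With three participants 24 hours apart and a 14-day review, a cohort takes at least 2 + 14 = 16 days. If Part 2 screening waits for Cohort 8 to clear, the last Cohort 3 participant is then at least 14 + 5 × 16 = 94 days past infusion. Only later-cohort returners could be screened early. Returners merely may be considered, so there may be none, and participants new to MGD014 are unaffected. All of this stands.
- **Footnote d** can be read as a rule on timing that schedules no sample. That is fair, but its mark sits on a Day 0 row with no ADA cell, so the table and the note still do not fit.
- **The ADA condition at Part 1 completion** is a second check. That sample is normally no later than screening, so it does not shorten the unsampled interval.
- **No SAP rule assigns such a case to multi-dosing.** If a returner's baseline were Part 1 Day 0, the Day 14 positive would be a genuine MGD014-induced conversion. Returners keep their participant identifier, so the two series can be linked. This also stands: the fault is an undefined baseline, not a wrong stated rule.

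**Conclusion.** The point holds as a gap in sampling and definition. The last ADA result before the first Part 2 infusion can be 56 days old, the blank Day 0 cell does not fit footnote d or Part 1 practice, and no ADA baseline is defined for Part 2 or for returners. Antibody from the Part 1 dose could then be credited to the multi-dose regimen. The 17-point shift assumes a Part 2-only denominator of six, which the SAP does not state; pooled over about 26 it is about 4 points. The probability cannot be fixed from the documents. It turns on the number of returners, on whether exclusion 20 covers MGD014, and on human onset timing.

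A reader might go further and infer that the plan lets sensitised people be re-infused while seropositive, as a safety failure. The documents do not support that. Exclusion 20 may prevent early re-screening, and the monkey timing comes from six weekly doses. The protocol also gives no safety rationale for exclusion 22, does not list a positive ADA among the events that stop infusions (5.3), and reports the monkey regimen as well tolerated although four animals became positive during dosing.

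**What to change.** 1. Add a Day 0 pre-infusion ADA sample to the Part 2 tables in Appendices 1 and 2, in line with footnote d and with Part 1.
2. In SAP 4.12 (and Protocol 14.8), define that sample as the Part 2 ADA baseline, and state the denominator for the conversion rate.
3. Report each returner's Part 2 ADA results together with the Part 1 series, so that the reader can see which exposure came before a conversion.
4. Reconcile exclusions 5, 20 and 22, Protocol 4.3 and the 56-day screening window as they apply to returners. What the eligibility rule should be is for the sponsor and investigator to decide.

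The cost is one extra tube per participant at a visit that already draws pre-infusion blood, at most six assays, and some table and SAP wording. The limit is that the Day 0 result may not be available before dosing. The sample corrects the baseline and does not necessarily gate the infusion.
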